Proposal

Serum thromboxane B2 Assay as a Measure of Platelet Production in Healthy Volunteers

Taking Aspirin

Short study name: COX-1 and TxB2

Principal Investigator: [name]

Laboratory Investigator: [name],

Co-investigators: [name], [name]^{1,2,3}, [name]^{1,2}, [name], [name]^{2,3}, [name].

Affiliations:

¹ Thrombosis and Atherosclerosis Research Institute (TaARI),

² Department of Medicine, McMaster University

³ Population Health Research Institute, Hamilton Health Sciences McMaster University

Overall objective:

To develop a valid method to quantify platelet production (without the use of radioactive isotopes) in order to examine the hypothesis that enhanced platelet production is a common cause of poor aspirin responsiveness in patients with atherothrombosis.

Specific objective:

To validate the Cayman Chemical serum thromboxane immunoassay as a measure of platelet production in healthy subjects who are treated with aspirin by demonstrating that the recovery of their serum thromboxane B2 levels occurs at a rate of about 10% per day after aspirin cessation.

Background and Rationale:

Cardiovascular disease is the most common cause of preventable death globally. Given once-daily, low dose aspirin reduces the risk of major cardiovascular events (MACE) by 25% in patients with atherothrombosis¹. By irreversibly acetylating cyclooxygenase-1 (COX-1) in platelets, aspirin blocks the production of thromboxane (TX) A₂, a potent stimulator of platelet aggregation, thereby mediating its anti-thrombotic effect. Despite its rapid clearance (30 minutes) from the circulation, the effect of aspirin on the inhibition of TXA₂ synthesis lasts for the lifespan of the platelet, which is about 10 days². In healthy subjects, a single 100-mg dose of aspirin inhibits almost 100 percent of TXA₂ synthesis within 30 to 60 minutes of its administration. TXA₂ synthesis then recovers slowly as the aspirin is cleared and new platelets with non-acetylated COX-1 ('unacetylated' platelets) are released from the bone marrow. Since only about 10% of platelets

Serum thromboxane B2 and platelet production

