are replaced daily by new platelets entering the circulation, at 24 hours after a dose of aspirin, TXA₂ synthesis is still suppressed by > 90%. At this level of suppression, TXA₂ mediated platelet aggregation remains maximally inhibited. So, provided that no more than 10% of 'unacetylated' platelets enter the circulation per day, once daily aspirin maintains an optimal antithrombotic effect.

Soon after aspirin was shown to be effective as an antithrombotic agent, several investigators reported that unlike healthy subjects, about a third of patients treated with aspirin showed incomplete suppression of TX synthesis or arachidonate-induced platelet aggregation³. These patients were called poor responders and subsequent studies showed that poor response to once daily aspirin, identified by either TX or by platelet aggregation assays, was associated with reduced antithrombotic effectiveness⁴. Several groups, including ours, proposed that, in certain conditions (e.g. post-coronary artery bypass grafting⁵, diabetes⁶, and essential thrombocythemia⁷), poor response to aspirin was caused by an increased rate of platelet production. Such a mechanism is a plausible cause of poor response to aspirin because an increased rate of platelet production would result in an increased proportion of 'unacetylated' platelets entering the circulation after aspirin is cleared, which would shorten the duration of platelet COX-1 suppression to <24 h. Because full suppression of TXA₂-dependent platelet function requires >90% inhibition of COX-1 activity, even a modest recovery of this activity can sustain a substantial platelet response⁸. Consistent with this proposed mechanism, we and others showed that a poor response to aspirin was reversed by giving aspirin twice daily (instead of once)^{6,7}. It is possible that an increased rate of platelet production is responsible for most cases

of poor response, in which case, the response could be restored by twice daily aspirin administration. Our ultimate aim is to test this hypothesis, but to achieve this aim we need to develop an accurate test of platelet production to identify patient groups that would benefit from twice daily aspirin.

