How can we identify patients in whom an increased rate of platelet production is responsible for poor response to aspirin? Previous methods to measure platelet production in healthy subjects, which were based on survival of radiolabeled platelets, have shown that platelets survive in the circulation for about 10 days. The **specific objective** of this study is to demonstrate that in healthy subjects in whom production of new platelets occurs at rate of 10% per day, the recovery of serum thromboxane B2 per day would be about 10%. Instead of labeling with radioactive isotopes, we will use the acetylation of platelet COX-1 by aspirin to identify the rate of platelet production. Our method is based on the observation that in normal subjects, after a single dose of aspirin, unacetylated COX-1 recovers at a rate of about 10 percent per day as new platelets enter the circulation⁹. However, measuring acetylation status of protein requires specialized proteomics assays. Instead, we intend to use an assay to quantify serum TXB2 as an indirect measure of the effect of unacetylated COX-1 from new platelets. If true, then the daily recovery of serum TXB2 would provide a readout of new platelet production.

The serum thromboxane B2 method has the additional advantage of providing information on both the rate of platelet production and the degree of platelet inhibition by aspirin. Such an advantage would facilitate the identification of non-responders whose reduced response is due

Serum thromboxane B2 and platelet production

to an increased rate of platelet production, as well as the assessment of response following aspirin dose modification in future studies.

Implications of this study:

Successful validation of serum thromboxane B2 assay performed in-house as a measure of platelet production will be critical to pursuing our multistep research program to: 1) investigate the frequency with which increased platelet production results in poor response to aspirin; 2) identify patient populations in whom increased production is a major cause of poor response to aspirin; 3) test the hypothesis that poor response in those populations can be overcome by twice daily aspirin; and 4) evaluate the effect of twice daily aspirin in those populations on reducing the risk of cardiovascular events.

Methods:

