Study design: Healthy volunteers will take aspirin 81 mg daily for 5 days. Serum thromboxane B2 (sTxB2) will be measured before taking aspirin (baseline), at 4h after last dosing (daily peak level), and then daily for 5 days after aspirin cessation.

Population: 20 healthy volunteers. Enrollment criteria are listed below:

- Inclusion criteria:
 - Healthy non-smoking volunteers;
 - Age \geq 18 years;
- Exclusion criteria:

Serum thromboxane B2 and platelet production

- Allergy or intolerance to aspirin;
- Current pregnancy;
- Use of aspirin or drugs interfering with platelet function (NSAIDs, anticoagulants) within one week of study enrolment.

Assays:

- Serum Thromboxane B2: serum TXB2 concentrations were measured using an enzyme immunoassay kit (Cayman Chemical, Ann Arbor, MI) according to the instructions provided by the manufacturer. In-house controls were tested with each batch.

Blood collection: 2.5 ml of blood in a serum tube for sTxB2 assay, and 3 ml of blood in EDTA for platelet count at baseline.

Statistical considerations:

- Sample size: As a pilot study, we plan to enroll 20 patients as recruitment of this number is feasible. This study will provide estimates of mean/median and variability (e.g. standard deviation and range) of serum thromboxane B2 and recovery in healthy volunteers and will inform on sample size calculation of future studies with this assay.
- Proposed analyses:
 - Biological variability of serum TXB2 will be represented as mean/median and standard deviation/range, at each time point of sampling.

Serum thromboxane B2 and platelet production

- Residual serum TXB2 will be plotted against time and recovery rate of serum TXB2 will be estimated, and compared with 10% rate of new platelet production reported in historic studies using radiolabeling method for detection.

Anticipated result:

In healthy subjects in whom production of new platelets occurs at rate of 10% per day, we expect a 10% increase in serum thromboxane B2 per day;

Study coordination, recruitment and logistics

This study will be performed at PHRI & TaARI. Healthy volunteers will be screened and recruited by the investigators or research assistants. Informed consent will be obtained from participants before we conduct our study. Samples will be collected by our research assistant or investigators and then transferred to TaARI for testing.

Role of the principal investigator

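### Does the expected 10% daily increase in serum thromboxane B2 put the trial's benchmark on the wrong scale?

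*Protocol*

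**What the plan says.** The Protocol gives the 10% target in several places.

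- Specific objective: "recovery of their serum thromboxane B2 levels occurs at a rate of about 10% per day after aspirin cessation".
- Background and Rationale: "the recovery of serum thromboxane B2 per day would be about 10" percent. The basis is that "platelets survive in the circulation for about 10 days" and that "unacetylated COX-1 recovers at a rate of about 10 percent per day as new platelets enter the circulation".
- Background and Rationale, on the state 24 hours after a dose: synthesis "is still suppressed by > 90" percent, explained by the replacement of only about a tenth of platelets each day.
- Study design: samples before aspirin, at 4 hours after the last dose, "and then daily for 5 days after aspirin cessation".
- Proposed analyses: "Residual serum TXB2 will be plotted against time and recovery rate of serum TXB2 will be estimated". The result is then compared with the 10% production rate from historical radiolabelling studies.
- Anticipated result: "we expect a 10% increase in serum thromboxane B2 per day".

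No passage says what the 10% is a percentage of, and none names a recovery curve. The section on the role of the principal investigator says that a detailed statistical analysis plan will be developed.

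**The concern.** The Anticipated result sentence makes serum thromboxane B2 itself the thing that increases by 10%, which in ordinary usage means growth on the current value. The biology in the rationale predicts a rise of about 10 percentage points of the unsuppressed level per day. Just after aspirin the level is close to zero, so the two scales are far apart. An assay that recovers exactly as hoped would miss the literal expectation, and one that hardly recovers would meet it.

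The curve looks like a second gap. Ten percent of baseline per day is a straight line, while 10% of the remaining deficit per day is a first-order curve. If neither is fixed in advance, agreement with 10% could depend on a fit chosen after the data are seen. Agreement with about 10% is the specific objective, and the protocol describes successful validation as critical to its later research programme.

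**Working it through.** **The plan's own figure.** A lifespan of about 10 days gives 1/10 = 10% of the platelet pool replaced per day. The 10% reproduces, as a share of the whole pool.

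**Scale.** Let r0 be the residual after the last dose, as a percentage of the pre-aspirin value. The protocol implies r0 below 10%; the values 1%, 2% and 5% are assumptions.

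- Literal reading, r0 × 1.1^5 on day 5: 1 × 1.611 = 1.6%; 2 × 1.611 = 3.2%; 5 × 1.611 = 8.1%. Even r0 = 9.9% gives only 15.9%.
- Points of baseline, r0 + 10 × 5 on day 5: 51%, 52% and 55%.
- Day-on-day rise if recovery is truly 10 points per day: on day 1, from 1 to 11 (+1000%) or from 5 to 15 (+200%). On day 5, 51/41 = +24% or 55/45 = +22%. It is never 10% within the sampling window.

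The literal reading is therefore incompatible with the rationale.

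**Which scale the protocol intends.** Set side by side, the passages agree:

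- The 24-hour statement links replacement of about a tenth of platelets to suppression above 90%. That holds only if both are fractions of the unsuppressed level.
- The objective and the rationale speak of recovery, which means return towards a starting level, and treat it as parallel to recovery of unacetylated COX-1.
- A pre-aspirin sample is planned, and the quantity to be plotted is residual thromboxane. A residual needs a reference, and the pre-aspirin value is the natural one.

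**Curve.** Noise-free data on days 0 to 5, with r0 = 0:

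| True recovery | Values, % of baseline | Straight-line fit | First-order fit |
|---|---|---|---|
| Linear | 0, 10, 20, 30, 40, 50 | 10.0 points/day | k = 0.138/day, 1 − e^(−0.138) = 12.9%/day |
| First-order, 100 × (1 − 0.9^t) | 0, 10, 19, 27.1, 34.4, 41.0 | 8.2 points/day | 10.0%/day |

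Other fitting methods, or leaving out day 0, move the off-model readings to 11.9–13.6 for linear truth and 7.7–8.6 for first-order truth. Quoting the rate constant instead of the daily fraction can raise the linear-truth reading to 14.6. A reading near 8 and a reading near 13 come from different true curves. For each curve the matching fit returns 10.

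**Sample times.** Linear recovery at 4 hours is 10 × 4/24 = 1.67 points. If that sample were coded as day 0 and the others as days 1 to 5, the slope would be 9.76 instead of 10.0, a loss of 2.4%. The protocol does not propose that coding.

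**The case for a change.** The best case for a change is that a benchmark should not have to be inferred. No passage writes the denominator, and the one sentence that states the expectation outright uses the wrong scale if taken at face value. The denominator is tied to the curve, the pilot's estimates are meant to inform later sample sizes, and the repair would cost only a few words.

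Part of this stands. The wording is loose, and writing that residual means percent of the participant's pre-aspirin value would be tidier. It does not go further, for four reasons.

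- The loose sentence is a forecast. The Proposed analyses line is what will be carried out, and it does not speak of an increase on the previous value.
- An analyst who tried the day-on-day reading would see rises of several hundred percent on day 1 and about 22% to 24% on day 5. That reading yields no single rate to compare with 10%.
- The planned samples support either scale and either curve, so nothing is lost by settling the definition in the statistical analysis plan.
- Making a linear slope primary is itself debatable. The lifespan is given only as about 10 days, and whether serum thromboxane tracks new platelets proportionally is what the study sets out to learn.

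**Conclusion.** No change to the plan is needed. The sentence under Anticipated result is imprecise, and read literally it would understate expected day-5 recovery by a wide margin: 1.6% to 8.1% of baseline against 51% to 55%, for assumed residuals of 1% to 5%. The rest of the protocol makes percent of the pre-aspirin level the evident meaning. The analysis line, followed as written by a competent analyst, gives a sound estimate on that scale.

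The choice of curve matters by about 2 to 4 points on a target of 10 (up to 4.6 if a rate constant is quoted). It is a detail commonly left to the statistical analysis plan, which is not at hand, so its absence from the protocol is not a fault. The study is a feasibility-sized pilot of 20 meant to provide estimates. It sets no significance test, margin or pass/fail rule against an approximate target.

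This conclusion assumes that residual thromboxane will be scaled to each participant's own baseline, as the design implies. The curve figures are noise-free and take the residual after the last dose as zero.
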